**Abstract**

The proposed study uses a sequential, multiple assignment randomized trial (SMART) to test an adaptive version of systems consultation consisting of academic detailing, practice facilitation, and physician peer coaching to increase the uptake of safer opioid prescribing practices at three levels of primary care (health system, clinic, prescriber). Academic detailing will be provided to all clinics and prescribers to inform prescribers on the goals of the study, the importance of improving opioid prescribing in primary care, and a review of the latest standards of prescribing guidelines. After three months, clinics will be randomized to receive nothing or receive practice facilitation where clinics will get an in-person or online visit and proceed with monthly teleconferences to improve clinic workflow related to opioid prescribing. Six months later, clinics will receive physician peer coaching that will employ two experienced addiction specialists who will provide guidance to prescribers dealing with tough patient panels. Additionally, this study aims to capture and analyze contextual factors that influence implementation in order to create a simple tool that will guide quality improvement in opioid prescribing. This SMART will deliver these three strategies to 40 primary care clinics from three health systems to compare the effect on average morphine milligram dose of an adaptive systems consultation implementation strategy compared to academic detailing alone over a 21 month time period. To our knowledge, this study would be the first to randomize at two levels to test the efficacy of the implementation of system consultation to improve opioid prescribing in primary care.

## **1. Background & Significance**

### **Importance of improving prescribing practices in primary care**

Opioids are commonly prescribed in primary care to relieve chronic pain. Although potentially effective for this purpose, accompanying burdens have become clear and widespread. In 2017, drug overdose was the leading cause of accidental death in the United States. Although the volume of opioids prescribed in the US declined each year from 2010 to 2015, about 3 times more opioids were prescribed per person in 2015 as in 1999, and prescribing rates still vary greatly, with the highest-prescribing counties prescribing 6 times more opioids per person than the lowest-prescribing counties. In 2015, 63.1% of drug-overdose deaths involved an opioid, and approximately half of opioid-related deaths involved prescription opioids. About half of opioid prescriptions are written in primary care. Clinical guidelines for opioid prescribing in primary care have been advanced, most notably the guidelines issued by the Centers for Disease Control and Prevention in 2016. Clinical guidelines have established consensus around a few basic ideas: (1) Physicians should discuss the risks and benefits of opioid therapy with patients by reviewing and signing formal treatment agreements before initiating the first opioid dose and throughout treatment. (2) Clinicians should avoid prescribing opioids in doses higher than 90-100 morphine milligram equivalent (MME) daily; evidence shows that patients with a dose of 100 MME or greater are 11 times more likely to die from overdose than patients taking doses less than 20 MME. (3) patients at increased risk for misuse (i.e., those with mental health or substance use disorders) are more likely to receive opioid prescriptions and higher doses; thus, screening for mental health and substance use disorders should be in place. (4) Opioid-benzodiazepine co-prescribing in any combination of doses should be avoided to reduce the risk of overdose. (5) Monitoring via urine drug testing should be instituted to ensure appropriate use of opioid medications.

### **Strategies for implementing evidence-based practices**

Despite the promotion of evidence-based practices (EBPs) related to opioid prescribing (and many other conditions), the healthcare system is notoriously slow in adopting EBPs. Lau et al. conducted a 2015 review of 91 studies aimed at determining the effectiveness of strategies for implementation of complex interventions in primary care settings. The most commonly used strategies were targeted at individual providers, generally demonstrating small to modest effects, with considerable variability between studies. The authors found little use of implementation strategies targeted at organizations or a wider context (e.g., health systems). Finally, the review found very limited data on the costs and cost-effectiveness of different implementation strategies should be used under what conditions, and that future research should study implementation strategies targeted at levels more broadly defined than individual providers. According to a systematic review focused specifically on the role of external change agents (e.g., coaches, facilitators, academic detailers, etc.) in primary care settings, the more successful implementation strategies tended to be those that offered regular, context-specific follow-up.

### **Systems consultation**

Systems consultation is a theoretically and empirically grounded, blended implementation strategy consisting of a bundle of 3 discrete strategies: (1) Academic detailing, in which an experienced physician provides recommendations and advice on how to improve clinical practice; (2) Practice facilitation, a team-based advising approach designed to tailor implementation to specific

clinical contexts; and (3) Physician peer coaching, in which an experienced physician provides one-on-one clinical advice on managing patient panels to other physicians (who may be less experienced with the selected clinical issue). Several other discrete strategies are also integrated into the systems consultation model, as categorized by Powell et al.'s (2015) taxonomy of implementation strategies, including: use of community-academic partnership, where leaders from an academic medical center work with community- based care clinics to improve the health of their communities; audit and feedback , which consists of providing performance feedback to clinics; conducting local assessments to determine the need for implementation; and tailoring implementation strategies to address potential barriers and facilitators.

### **Adapting implementation strategies to specific contexts**

Primary care clinics vary in their opioid prescribing practices and in their capacity to carry out implementation efforts. Clinics and prescribers are influenced by factors such as funding, regulations, geography, and policies. These considerations suggest that strategies for implementing EBPs will work differently in different clinics; moreover, different strategies might work best for different prescribers, depending on the prescriber's patient panel, experience in prescribing opioids, and other influences. Previous implementation research suggests that implementation strategies tailored to specific clinics are the most effective, although evidence also suggests that the effect of tailoring varies, and tends to be small to moderate. The literature does not specify the most effective approaches to adaptation or the cost-effectiveness of tailored strategies (compared with non-tailored strategies).

## **2. Study Objectives**

This study aims to understand the optimal sequencing and combination of implementation strategies that specific types of clinics and prescribers need to adopt clinical guidelines for opioid prescribing. The pragmatic goal is to give health systems a tool they can use to predict which clinics and prescribers will benefit most from which sequence and combination of implementation strategies. The bundle of strategies systems consultation consists of include academic detailing, practice facilitation, and physician peer coaching. We propose to recruit 40 clinics and 152 prescribers from 2 health systems for a sequential, multiple assignment randomized trial to receive academic detailing only, academic detailing + practice facilitation, academic detailing + practice facilitation + physician peer coaching, or academic detailing + physician peer coaching. We will use quantitative and qualitative analyses to compare outcomes of sequences and combinations with data collected every 3 months over the 21-month intervention period.

### **Primary Aim:**

Compare the effect of an adaptive systems consultation implementation strategy vs. academic detailing alone on average morphine milligram equivalent dose over 21 months.

### **Secondary Aims:**

- Develop an assessment of contextual factors that influence the effectiveness of different implementation strategies.

- Test 4 moderators and assess other factors that affect implementation to use to predict which implementation strategies will be most effective in different settings.
- Estimate the costs of delivering 4 different sequences and combinations of strategies, including the incremental cost effectiveness of adding facilitation and physician peer coaching.

## **Study Coordination**

The UW-Madison Implementation Science and Engineering Lab is the coordinating site for this study. The UW study coordinator will oversee all activities at the 40 clinics which include:

- developing site specific recruitment and data collection processes that meet study objectives;
- training site staff prior to the study on protocol procedures to maintain compliance with the protocol and human subjects regulation;
- communicating with site staff via monthly correspondence to monitor progress, inform of protocol changes/distribute new version of protocol, and address unanticipated issues or challenges;
- and manage all study data.

## **3. Selection of Subjects**

Patients are not the subject of the study. The subjects of study will be the clinic prescribers.

Prescriber panel data will be aggregated to the clinic and prescriber levels. To be included in the aggregated, de-identified prescriber panel data, patients must:

1. have a primary care provider at the clinic;
2. prescriptions for opioid therapy for at least 3 consecutive months;
3. and no cancer diagnosis or reception of hospice care.

**Clinics:** A total of 40 clinics will be recruited from primary care clinics of the two health systems: UW Health and Bellin Health. This protocol will detail the process at UW Health primary care clinics for which the HS IRB is the IRB of record. Bellin Health will follow similar procedures with oversight from the UW study coordinator.

Clinics will be eligible for the study if they:

1. are a primary care clinic (non-pediatric primary care, internal medicine, or family medicine);
2. have not received the systems consultation intervention; and
3. do not explicitly prohibit initiating opioid therapy.

**Change team:** Up to 7 team members will be recruited and consented to participate in practice facilitation. Change teams include a change team leader (likely a clinic medical director or other clinician) and supporting clinic staff such as nurse practitioners, physician assistants, registered nurses, lab technicians, and medical assistants.

**Prescribers:** de-identified patient data will be aggregated at the level of the prescriber and clinic. In this context, prescribers will be known to the study team only by the code number assigned to them by HIP. Data will be obtained only from those clinicians who:

1. are primary care physicians or other providers with prescribing privileges;
2. are not temporary providers who do not manage stable panels or patients;

## **4. Registration Procedures**

### **Clinic Recruitment**

The study team will discuss the study with health system leaders who gave letters of support and identify clinics that may be interested in participating. The study team will present the study to clinicians at an all-provider meeting to build awareness and inform clinics that this study is available to join. Health care leaders will send an email on behalf of the study team to clinic medical directors of the health system. The email will notify medical directors that research is being done at clinics of their health system and instruct them how to opt-out if they wish to decline participation in the study and future contact from the study team. The email will instruct medical directors to direct any questions they have to the study team.

Medical directors who choose not to opt-out of the study will be invited via email to attend the regional academic detailing meetings. Medical directors will be asked to forward the email to any clinic staff who may be interested in participating in the academic detailing meeting. The email will instruct interested medical directors and clinic staff to call the study team if they are interested in attending or have any questions. Clinics will be asked to allow medical directors and interested clinic staff to attend regional academic detailing meetings on clinic time where the study team will explain the study objectives and participation expectations. Medical directors and clinicians will sign consent forms and will be handed information sheets after the study is explained, but before further information about opioid prescribing is presented. Those attending the academic detailing meeting via webinar will be sent the consent form electronically and sign and return the consent form before the meeting. All signed consent forms will be sent via email, fax, or postal service to the study team. Medical directors will be assured that there is no obligation to participate in the study and that their decision is voluntary. The study team will explain to medical directors that the clinic and clinicians can drop out from study participation at any time and that their clinical practice will in no way be affected by their choice to participate or not.

### **Staff Recruitment**

Following the academic detailing meeting an email will be sent out to all clinic staff by the medical director of behalf of the study team. The email will inform clinic staff that research may be conducted at their clinic, what the research activities they may be asked to participate in include, and that they should contact the study team if they have any questions. While clinicians have the opportunity to opt-out of individual-level activities, they still may be involved in the research by virtue of doing their jobs in a clinic where the study is occurring. In a separate email the study team will provide the clinicians who could not make the academic detailing meeting with a link to a webinar. The study team will ask prescribers and clinicians who may participate on the change team who are interested in participating in the study to watch the webinar and sign the consent form. All signed consent forms will be sent via email, fax, or postal service to the study team.

The study team will call medical directors of clinics that have been randomized to receive practice facilitation to schedule the online or in-person clinic visit and ask the medical director to identify individuals who might be interested in participating on a change team. The medical director will

identify an appropriate individual who might be interested in being a change team leader, and up to 5 additional clinicians to serve as change team members. At the online or in-person clinic visit the study team will provide change team members with a virtual or hard copy information sheet about practice facilitation. The information sheet will inform change team members what is required of them and that their participation is voluntary. The change team will be told that there is no obligation to participate and that their clinical practice will in no way be affected by their choice to participate or not. The study team will assure clinicians that they can take their time to think about their participation and may leave the practice facilitation at any time. While most future meetings are anticipated to be virtual, any face-to-face contacts with clinician subjects will take place at the regional meeting, in the clinician subject's office or in a private room in the clinic at a convenient time for the clinician subject. Virtual meetings will be held securely over WebEx. Online practice facilitation sessions will be recorded to review for notes and accuracy. Notes will be kept securely on Box and recorded sessions will be destroyed.

## **Consent**

A request for a waiver of informed consent will be made for health system leaders and for clinic staff in clinic-level interventions. The study team will ask health system leaders to send out an email on behalf of the study team, informing medical directors about the research and the ability to opt-out of future communication with the study team. Medical directors who do not opt-out by a specified date on the email will be invited to the academic detailing meetings and have the ability to forward the email to other interested clinicians. These subjects will sign consent forms and receive a study information sheet at the academic detailing meeting. Those attending the meeting via webinar will be asked to read, sign, and return consent forms prior to the meeting. Webinar attendees will send the signed consent form to the study team via email, fax, or mail.

After the academic detailing meetings, the medical director will send out an email on behalf of the study team to notify clinic employees that research may be done at their clinic and that they have the option to opt-out of the study activities. The study team will consent any prescriber and clinic staff who did not attend the academic detailing meeting, but wish to participate in the study via email. Prescribers will be sent an email with a link to the webinar of the academic detailing meeting and a consent form to read and sign. Prescribers will send the signed consent form to the study team via email, fax, or mail.

If participants decide to no longer participate in the study they will contact the PI, [name], to rescind their consent. Data that is already collected will be retained for analyses, but no further data of that participant will be provided to the study team.

A waiver of signed consent will be requested for qualitative interviews. Participants will be invited over email to participate in interviews. After a week, if the participant does not respond to the email the study team will call the participant to invite them to the study. The study team will call once. If there is no answer a new invite will be sent to a different participant. Participants who agree to be interviewed will be sent information sheets to read. This consent process is supplemental from the consent process participants went through at or before the educational meeting.

## **Randomization**

Randomization will take place at the clinic level at month 3 (practice facilitation) and month 9 (physician peer coaching). A research team member will conduct the randomization using the urn randomization program.

Randomization of clinics will take place at intervention month 3 on a 1:1 ratio to assign clinics that will receive practice facilitation plus academic detailing or academic detailing only. At intervention month 9 all clinics will be randomized on a 1:1 ratio to assign clinics who will receive the current intervention strategy plus physician peer coaching or continue the current intervention strategy for 12 months. Randomizations will be stratified on clinic's 1) health system, 2) number of patients, and 3) average MME being greater or equal to the health system's clinic average.

## **5. Intervention Plan**

While the intervention plan is continuing as intended, due to the COVID-19 pandemic, study intervention activities were put on hold between March 25th and July 15th. Study activities have since resumed as intended.

Subjects will receive a combination of the following strategies:

**Academic detailing.** Clinicians from participating clinics will be invited to a regionally hosted, in-person training session where they will be provided lunch. The study team will also have a webinar option (such as WebEx) for clinicians who cannot travel to the regional in-person meeting. The session will be designed to both inform and engage clinic staff in the study. The session will be led by [name] and [name], who are experts in addiction medicine with extensive experience managing the care of long-term opioid patients. Invitees will be medical directors and prescribers (physicians, nurse practitioners, physician assistants), nurses, and staff directly involved in clinic workflows related to opioid prescribing (e.g., medical assistants, lab techs, etc.). We will ask each clinic to designate the clinic medical director to serve as contacts for the research team. The training will cover the goals of the study, the importance of improving opioid prescribing in primary care, a review of the latest standards of guidelines concordant care, how improvements in clinic workflows can affect patient outcomes, clinical topics such as how to address opioid-induced hyperalgesia and balancing patient-reported pain and function during dose reduction, and trainings on how to use electronic medical records to monitor key opioid prescribing outcomes. An assessment will be conducted during the session to elicit contextual characteristic that use the electronic health record to monitor key opioid prescribing outcomes. The assessment will be a survey given at meetings or online (for those joining via webinar)s. If clinicians are watching the academic detailing meeting on their own or via webinar, they can take the survey on REDCap. At the conclusion of the initial meeting, clinicians who attended the meeting will be asked to form change teams at their clinics.

A quarterly hour-long academic detailing meeting will be hosted via webinar (such as WebEx) to provide clinics and clinicians further information about the CDC opioid prescribing guidelines. Quarterly webinar meetings will be separate for each study arm.

Following the academic detailing meeting, the health systems will create and deliver audit & feedback reports to clinicians. Health systems are already doing this and will customize the reports to fit the study. These reports will let clinicians know about their clinic's opioid prescribing metrics such as average MME, % of patients with urine drug testing, treatment agreements, and mental health screens, and % of patients co-prescribed benzodiazepines. Reports will only be at the clinic level.

**Practice facilitation.** Research staff trained in practice facilitation and/or study team members will meet virtually with clinics using WebEx (or visit clinics in-person) and follow up over the course of up to 5 monthly then 4 quarterly videoconferences or teleconferences to help clinics improve processes related to opioid prescribing, such as ensuring that treatment agreements are signed by prescribers and patients at least once a year, and integrating urine drug testing into clinic workflows. Clinic medical directors will create change teams consisting of the clinic medical director and a physician change leader and up to 5 clinic staff. The online or in-person visit will begin with a meeting with the clinic medical director and the change team leader. At the meeting the facilitator will set a plan for the day and answer any questions about the meeting. The facilitator will tour the clinic in-person or virtually over WebEx. The facilitator will then meet (in-person or virtually) with the change team for an hour to cover how to make workflow changes such as integrating treatment agreements and urine drug tests into clinic processes. The change team will be educated about the nominal group technique and Plan-Do-Study-Act cycles (PDSA cycles) to select the area of improvement for the first PDSA cycle. The practice facilitator will assist the change team in filling out the PDSA cycle and the practice facilitator will enter the info into the Change cycle data table for reference for the follow-up conference call. Then the facilitator will debrief with the medical director and change team leader to discuss the next steps for follow-up discussions. Over the next 18 months clinics will be able to call in or meet over WebEx for up to 5 monthly, 60 minute-long meetings, followed by 4 quarterly hour-long follow-up discussions about the workflow changes. Sessions will be recorded using encrypted audio recorders or WebEx's recording feature. Recordings will be used to ensure accurate note taking. Recordings from audio recorders will be stored on the facilitator's password-protected computer or laptop. Once note taking is completed the recordings will be destroyed.

**Physician peer coaching.** At UW Health, physician peer coaches will be [name]. At Bellin Health, physicians with relevant experience in opioid prescribing will be nominated by health system leaders to become each systems' physician peer coaches. These coaches will become members of the research team. [name] help their peers manage their patients on opioid therapy. Participating clinics randomized to physician peer coaching will receive up to 4 quarterly coaching sessions over 12 months. Physician peer coaches will provide help to prescribers to assist with tough panels through up to four quarterly coaching sessions over 12 months. Coaching consultations will occur in sessions via videoconference (WebEx) or teleconference. Participants attending the physician peer coaching sessions will be asked to take a survey before each session to let the coach know what topics the group needs help with. After each physician peer consulting session, participants will be asked to complete a post-session survey to assess how the session was received and how confident the participant feels about addressing the session topic with patients. After the fourth and last session, participants in the physician peer consultation interventions will be asked to take a final survey to evaluate how the intervention impacted their confidence and experiences treating patients prescribed opioids for chronic pain, and feedback on the intervention itself.

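### The initial academic detailing meeting asks clinicians from all clinics to form change teams before the month-3 randomization, although the plan elsewhere makes the change team part of practice facilitation

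*Combined protocol and SAP*

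**What the plan says.** The Abstract gives the order of events. First, "Academic detailing will be provided to all clinics and prescribers". Then, "After three months, clinics will be randomized to receive nothing or receive practice facilitation". The Randomization section confirms the timing: "Randomization of clinics will take place at intervention month 3 on a 1:1 ratio". It adds a second step: "At intervention month 9 all clinics will be randomized on a 1:1 ratio".

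The academic detailing paragraph of section 5 (Intervention Plan) states that, when the initial meeting ends, "clinicians who attended the meeting will be asked to form change teams at their clinics". It makes no distinction by arm.

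Three other places tie the change team to practice facilitation:

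- Section 3 (Selection of Subjects), under the change team entry: "Up to 7 team members will be recruited and consented to participate in practice facilitation".
- Staff Recruitment in section 4: the study team telephones "medical directors of clinics that have been randomized to receive practice facilitation" to schedule the visit, and asks them to name a leader and members.
- The practice facilitation paragraph of section 5: "Clinic medical directors will create change teams consisting of the clinic medical director and a physician change leader and up to 5 clinic staff".

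The qualitative paragraph under Data collection plans interviews with two change team leaders from each intervention group at each health system, 8 in all.

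**The concern.** The primary aim compares the adaptive strategy with academic detailing alone, and the Power section sizes the trial for all three strategies against academic detailing only. The comparator therefore has to be kept free of elements that belong to the strategy under test. A change team is such an element, since it is the group through which a clinic carries out workflow changes in practice facilitation.

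The request sits inside academic detailing, before any clinic has an assignment, so it would reach clinics that later receive detailing only or detailing plus coaching. It would come in a session that already covers workflow improvement and the use of electronic records to monitor prescribing, and clinic-level feedback reports follow. A clinic that acted on it would have a team, a topic and data, though no facilitator. The plan does hold the quarterly webinars separately by arm, but the team request has no such separation.

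At stake are what the reference sequence actually is, the size of the primary contrast and of the facilitation effect, and possibly one planned moderator, clinic-level experience of quality improvement, which is assessed again at months 5, 9 and 21.

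**Working it through.** **1. The passages side by side**

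| Place | Who is asked | When |
|---|---|---|
| Section 5, academic detailing | Attendees from any clinic | Initial meeting, before month 3 |
| Section 4, Staff Recruitment | Medical directors of facilitation clinics | After the month-3 randomization |
| Section 5, practice facilitation | Medical directors, under the facilitation heading | Not stated |
| Section 3, change team | Members recruited for facilitation | Not stated |

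The first two rows cannot both describe how teams are formed. Nothing exempts clinics assigned to academic detailing only, or tells them to stand a team down.

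**2. The interview count.** Taken literally, two leaders per group at each of two systems, with 8 in total, gives 8 / (2 × 2) = 2 groups with change teams. Four groups would give 2 × 2 × 4 = 16. The count fits teams in the two facilitation groups only. It is supporting evidence and not proof, because the sentence could also be read as two leaders per group over four groups (2 × 4 = 8).

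**3. The plan's sample size.** Inputs from the Power section: d = 0.66, intraclass correlation 0.14, m = 4 prescribers per clinic, type I error 5%, early adoption rate p = 0.50, 80% power, 40 clinics. The section prints no formula and does not say whether the test is two-sided. I assume a two-sided test and a cluster formula with an inflation factor f = 1 + (1 − p) = 1.5:

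- Design effect = 1 + (4 − 1) × 0.14 = 1.42
- K = 4 × (1.960 + 0.842)² × 1.42 × 1.5 / (4 × 0.66²) = 38.4, so 39 clinics
- With m = 152 / 40 = 3.8, K = 39.6, so 40 clinics

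This reproduces the stated 40. At 40 clinics and m = 4, SE = √(4 × 1.5 × 1.42 / (4 × 40)) = 0.2308, and power = Φ(0.66 / 0.2308 − 1.96) = Φ(0.90) = 0.82.

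**4. A second basis.** Two 1:1 randomizations of all 40 clinics leave about 10 clinics per sequence, which corresponds to f = 2. Then SE = √(4 × 2 × 1.42 / (4 × 40)) = 0.2665, and power = Φ(0.66 / 0.2665 − 1.96) = Φ(0.52) = 0.70.

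**5. Illustrative dilution.** The documents give no share of the effect due to having a team, so the losses below are assumptions. If no teams form, the loss is zero.

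| Assumed loss of contrast | d | Power, f = 1.5 | Power, f = 2 |
|---|---|---|---|
| 0% | 0.660 | 82% | 70% |
| 5% | 0.627 | 78% | 65% |
| 10% | 0.594 | 73% | 61% |
| 20% | 0.528 | 63% | 51% |
| 30% | 0.462 | 52% | 41% |

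**The case against.** The strongest reply is that section 5 describes a request and nothing more. No text shows a team forming, meeting or acting outside a facilitation clinic, and the recruitment steps suggest that none was intended: directors of facilitation clinics would hardly need to be asked for members if teams already existed. Staff Recruitment also speaks of clinicians who might join a change team when it describes consent after the detailing meeting. Candidates could thus be lined up early and teams activated only where facilitation is assigned. The text allows that reading, but section 5 does not state it, and staff running the meeting would follow section 5.

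A reader might infer that the comparator is contaminated with practice facilitation and that the primary result is biased. The documents do not support that, for three reasons:

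- The facilitator visit and tour, the teaching on the nominal group technique and PDSA cycles, and the monthly and quarterly follow-up meetings stay with facilitation clinics.
- Section 3 and the facilitation paragraph describe the team as belonging to facilitation, but neither says that teams form only there.
- A request made to every clinic before allocation leaves the randomized comparison valid for adding facilitation and coaching to detailing as delivered. What changes is the meaning of the comparator and, possibly, the size of the contrast.

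A reader might also take 70% as the plan's own starting power. It is not: it leaves out the 50% early adoption rate, with which power is about 82%. Which basis suits this design is a separate question.

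**Conclusion.** The contradiction is real and touches the definition of the reference sequence. As written, section 5 asks all clinics, before randomization, to set up a component that the rest of the plan places in practice facilitation. The consequence is conditional: if the request is made, and if teams form and act in clinics without facilitation, those clinics receive more than academic detailing alone, and both the primary contrast and the facilitation effect could shrink.

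The size is unknown. The power figures show sensitivity only and rest on assumed losses, a two-sided 5% test, a normal approximation and a formula inferred because it reproduces the stated 40 clinics. On the Power section's inputs the margin over 80% is small enough that an assumed 5% loss would use it up. The point merits correction because the remedy costs almost nothing and protects the main comparison. It is not evidence that the comparison has failed.

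**What to change.** Reconcile the academic detailing paragraph of section 5 with Staff Recruitment and the practice facilitation paragraph. Remove the team request from the initial meeting, and state that change teams are requested only after the month-3 randomization and only in clinics assigned to practice facilitation. Change the meeting script to match.

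Section 5 says that study activities resumed after a pause, so some initial meetings may already have taken place. For those, deleting the sentence would hide what was delivered. State instead what attendees were asked, record which clinics without facilitation formed a team, and report this with the primary result. One item in the scheduled month 5, 9 or 21 assessment would do. The contact logs may not suffice, because they cover contacts by staff delivering the strategies and need not capture teams in clinics without a facilitator.

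The cost is a one-sentence edit, a script change and one small extra data item. No additional clinics are needed.
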